Female subjects of childbearing potential and male subjects must agree to either continue abstinence from sexual intercourse or utilize protocol specified methods of contraception if they choose to engage in intercourse from the screening/enrollment visit throughout the study period and for 30 days following the last dose of study drug (90 days for males). Female study subjects of childbearing potential will undergo regular pregnancy testing while taking presatovir. The investigator will counsel subjects on the protocol specified method(s) for avoiding pregnancy in case the subject chooses to engage in heterosexual intercourse.

Abstinence is an acceptable method only when this is in line with the preferred and usual lifestyle of the subject. Periodic abstinence (eg, calendar, ovulation, symptothermal, postovulation methods), declaration of abstinence for the duration of a trial, and withdrawal (coitus interruptus) are not acceptable methods of contraception.

Protocol specified contraceptive methods are as follows: (1) a combination of one hormonal method and one barrier method; or (2) use of an intrauterine device (IUD) or tubal sterilization; [Appendix Table 1](#) below. Acceptable hormonal methods include injectable progesterone, progesterone implants, combination oral contraceptives, transdermal contraceptive patch, and vaginal ring. Acceptable barrier methods include diaphragm with spermicide, cervical cap with spermicide, and the male condom with spermicide. Female subjects must use either a hormonal method or a barrier method if the partner has a vasectomy and the male partner should be the sole partner for that subject. For a vasectomy, appropriate post-vasectomy documentation of the absence of sperm in the ejaculate must be available. If a subject has undergone tubal sterilization or has had a Copper T 380A IUD or LNG 20 IUD inserted, no other contraception is needed.

If tubal sterilization is via the Essure procedure, verification of tubal blockage by hysterosalpingogram (HSP) must be performed approximately 3-months after microinsertion. Prior to verification, Essure is not considered a reliable form of contraception and the contraception methods described below must be used. Female subjects who utilize hormonal contraceptives as one of their birth control methods must have used the same method for at least 3-months before study dosing.

Appendix Table 1. Protocol Specified Contraceptive Methods

Methods to Use by Themselves	Combination Methods	
	Hormone Methods (choose one and use with a barrier method)	Barrier Methods (choose one and use with a hormone method)
Intrauterine Devices (IUDs) 
 • Copper T 380A IUD • LNG 20 IUD 	Estrogen and Progesterone 
 • Oral contraceptives • Transdermal patch • Vaginal ring Progesterone 
 • Injection • Implant 	
 • Diaphragm with spermicide • Cervical cap with spermicide • Male condom (with spermicide)
Tubal Sterilization	Partner's vasectomy must be used with a hormone or barrier method and the male partner should be the sole partner for that subject. For a vasectomy, appropriate post-vasectomy documentation of the absence of sperm in the ejaculate must be available.	

The investigator will counsel all subjects on the most effective method(s) for avoiding pregnancy during the study.

4) Additional Requirements for Male Subjects

Male subjects must agree to use condoms during heterosexual intercourse and avoid sperm donation while enrolled in the study and for at least 90 days after administration of the last dose of study medication.

Use of condoms has been proven to decrease the risk of transmission of HIV and other sexually transmitted diseases. The use of spermicide is not recommended if the subject or subject's partner is infected with HIV.

5) Procedures to be Followed in the Event of Pregnancy

Subjects will be instructed to notify the investigator if they become pregnant at any time during the study, or if they become pregnant within 30 days of last study drug dose. Subjects who become pregnant or who suspect that they are pregnant during the study must report the information to the investigator and discontinue study drug immediately. Subjects whose partner has become pregnant or suspects she is pregnant during the study must report the information to the investigator.

Instructions for reporting pregnancy, partner pregnancy, and pregnancy outcome are outlined in Section 7.7.2.1.

## LIST OF ABBREVIATIONS

AE	adverse event
ALT	alanine aminotransferase
ANCOVA	analysis of covariance
AST	aspartate aminotransferase
ATC	Anatomical Therapeutic Chemical (drug class)
BLQ	below the limit of quantification
BMI	body mass index
CI	confidence interval
CSR	clinical study report
DAVG	difference between time-weighted average post-baseline and baseline
DMC	Data Monitoring Committee
ECG	electrocardiogram
eCRF	electronic case report forms
EOT	end of treatment
FAS	Full Analysis Set
FLU-PRO	patient-reported outcome (PRO) measure to standardize the assessment of influenza (FLU) symptoms in clinical studies
HLT	high level term
HLGT	high level group term
ICH	International Conference on Harmonisation
ICU	Intensive Care Unit
ID	identification
IMP	investigational medicinal product
IWRS	Interactive Web Response System
LLT	lower level term
LT	lung transplant
LOQ	limit of quantification
MedDRA	medical dictionary for regulatory activities
ml	milliliter
MMRM	mixed-effect model with repeated measures
PD	pharmacodynamics
PK	pharmacokinetics
PP	Per Protocol
PT	preferred term
Q1	first quartile
Q3	third quartile
RSV	respiratory syncytial virus
RT-qPCR	quantitative real time polymerase chain reaction
SAP	statistical analysis plan

SD	standard deviation
SE	standard error
SOC	system organ class
TEAE	treatment-emergent adverse event
TFLs	tables, figures, and listings
WHO	World Health Organization

## 1. INTRODUCTION

This statistical analysis plan (SAP) describes the statistical analysis methods and data presentations to be used in tables, figures, and listings (TFLs) in the clinical study report (CSR) for Study GS-US-218-1797. This SAP is based on the study protocol amendment 2 dated 12 September 2016 and the electronic case report forms (eCRF). The SAP will be finalized before the database finalization. Any changes made after the finalization of the SAP will be documented in the CSR.

### 1.1. Study Objectives

The primary objective of this study is as follows:

- To evaluate the effect of presatovir (GS-5806) on nasal RSV viral load in RSV-positive lung transplant (LT) recipients with acute respiratory symptoms

The secondary objectives of this study are as follows:

- To evaluate the effect of presatovir on clinical sequelae of RSV infection and on measures of lung function
- To evaluate the pharmacokinetics (PK), safety, and tolerability of presatovir

### 1.2. Study Design

This is a randomized, double-blind, placebo-controlled study evaluating the effect of presatovir on efficacy, PK, safety, and tolerability in LT recipients with RSV infection.

Approximately 60 RSV positive subjects with acute respiratory symptoms will be enrolled from approximately 40 centers. All subjects will be permitted to receive the standard-of-care therapy for RSV infection per their local medical practices, in addition to the investigational medicinal product (IMP).

Subjects will be randomized in a 2:1 ratio to receive presatovir administered as a 200-mg dose on Day 1/Baseline, followed by a 100-mg dose daily on Days 2 through 14 or placebo-to-match (PTM) once daily for a total of 14 days. Subjects will be stratified by 2 factors:

[figure not shown]
- Treatment of RSV infection (yes or no) with ribavirin (oral, intravenous, or aerosolized)
- Use of palivizumab or IVIG (yes or no)

Subjects will be followed for a total of 28 days in the main study, during which a total of 8 study visits will be performed to assess safety, tolerability, PK, and viral loads. PPD

**Figure 1-1. Study Visits**

### 1.3. Sample Size and Power

Sample size calculations are based on results observed from 3 studies:

- 1) A study that evaluated the efficacy of oral and aerosolized ribavirin treatment for preventing progression from upper to lower respiratory tract infection in hematopoietic cell transplant recipients with RSV infections (unpublished data from [name])
- 2) A study conducted by Zamora et al that evaluated the treatment of RSV infection in LT recipients
- 3) GS-US-218-1227, an on-going Phase 2 study that is evaluating the antiviral effects of presatovir in hospitalized adults with RSV infection.

The sample size calculation assumes the time-weighted average change in RSV log10 viral load from Day 1/Baseline through Day 7 in the placebo group will be -1.5 log10 copies/mL with a corresponding standard deviation (SD) of 1.2. Based on these assumptions and the 2:1 allocation ratio to receive presatovir or placebo, with 34 subjects in the presatovir group and 17 subjects in the placebo group, there is at least 85% power to detect a 1.2 log difference in time-weighted average change in log10 viral load between presatovir and placebo using a 2-sided 0.04-level test in the co-primary endpoint including all subjects in the Full Analysis Set (FAS). There is 85% power to detect a 1.5 log difference with 17 subjects in the presatovir group and 9 subjects in the placebo group in the co-primary endpoint analysis of the subjects in the FAS with ≤ median duration of RSV symptoms prior to the date of the first dose of study medication in the overall population using a 2-sided 0.017-level test, assuming a SD of 1.2. Given an evaluable rate of 85%, a total of 60 subjects will need to be randomized into the study.

## **2. TYPE OF PLANNED ANALYSES**

### **2.1. Data Monitoring Committee Analysis**

An external multidisciplinary Data Monitoring Committee (DMC) will review the progress of the study and perform interim reviews of safety data in order to protect subject welfare and preserve study integrity. To ensure the best interests of the participants, the DMC will recommend to the sponsor if the nature, frequency, and severity of adverse effects associated with study treatment warrant the early termination of the study, the continuation of the study, or the continuation of the study with modifications.

The DMC's role and responsibilities and the scope of analysis to be provided to the DMC are provided in a mutually agreed upon charter, which defines the DMC membership, meeting logistics, and meeting frequency.

One safety review was originally scheduled to occur after approximately 50% of the planned 60 subjects had been enrolled and had completed Day 28 visit or discontinued the study. This DMC review was cancelled due to the reasons specified in Section 7.7.

### **2.2. Main Study Analysis**

After all subjects have completed the main study portion, outstanding data queries have been resolved or adjudicated as unresolvable, and the data from the main portion of the study has been cleaned and finalized, the study blind will be broken and the analysis of the data collected at the main study portion will be performed.

### **2.3. Final Analysis**

After subjects who chose to participate in the optional registry have completed the study, and all data have been cleaned and finalized, the final analysis of the data will be performed.

### **3. GENERAL CONSIDERATIONS FOR DATA ANALYSES**

Analysis results will be presented using descriptive statistics. For categorical variables, the number and percentage of subjects in each category will be presented; for continuous variables, the number of subjects (n), mean, standard deviation (SD) or standard error (SE), median, first quartile (Q1), third quartile (Q3), minimum, and maximum will be presented.

By-subject listings will be presented for all subjects in the relevant analysis sets and sorted by subject ID number, and visit date. Data collected on log forms, such as AEs, will be presented in chronological order within the subject. The treatment group to which subjects were randomized will be used in the listings. Age, sex at birth, race, and ethnicity will be included in the listings, as space permits.

#### **3.1. Analysis Sets**

Analysis sets define the subjects to be included in an analysis. Analysis sets and their definitions are provided in this section. Subjects included in each analysis set will be determined before the study blind is broken for analysis. The analysis set will be identified and included as a subtitle of each table, figure, and listing.

For each analysis set, the number and percentage of subjects eligible for inclusion, as well as the number and percentage of subjects who were excluded and the reasons for their exclusion, will be summarized by treatment group.

A listing of reasons for exclusion from analysis sets will be provided by subject.

##### **3.1.1. All Randomized Analysis Set**

All Randomized Analysis Set includes all subjects who were randomized in the study.

##### **3.1.2. Full Analysis Set**

The Full Analysis Set (FAS) includes all randomized subjects who took at least 1 full dose of study drug, and have an RSV viral load greater than or equal to the lower limit of quantification (LLOQ) of the RT-qPCR assay in the Day 1/Baseline nasal sample, as determined by RT-qPCR at the central lab. The subgroup analysis set includes subjects in the FAS who have the duration of RSV symptoms prior to the date of the first dose of study medication  $\leq$  a median value of the distribution of the duration of RSV symptoms in the overall FAS population. The FAS and the subgroup analysis set will be used as the primary analysis sets for efficacy analyses.

### **3.1.3. Per Protocol Analysis Set**

The Per-Protocol (PP) Analysis Set includes subjects in the FAS who meet the following criteria:

- Did not violate the following major exclusion criteria (EC)
  - EC #2: Use of a strong or moderate cytochrome P450 enzyme (CYP) inducer within 2 weeks prior to drug dosing
  - EC #16: An estimated eGFR  $<30$  mL/min/1.73m^2 obtained  $\leq 7$  days prior to Screening
  - EC #17: ALT or AST  $> 5$  times the ULN obtained  $\leq 7$  days prior to Screening
  - EC #18: Clinically significant elevations in total bilirubin (TB)
- Did not violate the following major inclusion criteria (IC)
  - IC #3: Had new onset respiratory symptoms or acute worsening of chronic preexisting symptoms  $\leq 7$  days prior to IMP administration on Day 1/Baseline
- Missed  $\leq 2$  doses (4 tablets) over the course of treatment
- Missed  $< 3$  nasal swab samples over the course of the study

The PP Analysis Set is the secondary analysis set for efficacy analyses.

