1.2.4.5. Study GS-US-218-1409

Study GS-US-218-1409 is a Phase 1, single-center, single and multiple dose study to evaluate the effects of a multi-transporter inhibitor cyclosporine (P-gp, BCRP, OATP1B1/1B3) o p-, a potent prototypical inducer rifampin (CYP3A and P-gp) or a moderate inducer efavirenz (CYP3A) on the PK of presatovir in healthy subjects. Forty-nine healthy males and females of non-childbearing potential who are 18 to 55 years of age were enrolled.

A total of 26 of 49 subjects (53.1%) experienced AEs. All events reported in this study were Grade 1. There were no SAEs, deaths, or discontinuations due to AEs. Dizziness was the most frequently experienced AE, reported by a total of 12 subjects in Cohort 4 and no subjects in Cohort 1 or 2. All AEs of dizziness occurred while subjects were receiving efavirenz and not during treatment with presatovir.

Most laboratory abnormalities were Grade 1 or 2, and all Grade 3 laboratory abnormalities were related to cholesterol. All liver function test elevations were Grade 1. No notable differences with regards to laboratory findings, vital signs, or other safety evaluations were noted between treatment groups. For additional information, refer to the presatovir IB.

Co-administration of a single-dose cyclosporine resulted in a minor increase in presatovir plasma exposures (10.6% in C_{max} and 26.1% in AUC_{inf}), suggesting that presatovir is not a sensitive substrate of efflux transporters P-gp and BCRP or hepatic uptake transporters OATP1B1 and OATP1B3. Multiple doses of rifampin or efavirenz decreased presatovir exposures to various degrees. Rifampin decreased presatovir C_{max} and AUC_{inf} by approximately 40% and 83%, respectively. Decreases in exposure were coupled with a rifampin mediated reduction in the median $t_{1/2}$ of presatovir (32.9 to 13.4 hours). Multiple doses of efavirenz slightly decreased presatovir C_{max} by approximately 13% and significantly reduced presatovir AUC_{inf} by 56%. The median $t_{1/2}$ of presatovir was shorter in the presence of efavirenz (33.5 to 17.9 hours). Collectively, these results suggest that presatovir clearance is sensitive to CYP3A induction by moderate or strong inducers of these pathways.

Taken together, these analyses suggest that presatovir can be coadministered with inhibitors of P-gp, BCRP, OATP1B1, or OATP1B3 without dose modification. Co-administration of moderate or potent inducers of CYP3A is not recommended.

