1.4. Dose Rationale

The dose and administration schedule selected for this study is a single dose of 200 mg presatovir administered orally or via NG tube on Day 1/Baseline, followed by 100 mg once daily on Days 2 through 14. This regimen was selected based upon the PK characteristics of presatovir and the pharmacokinetic/pharmacodynamic (PK/PD) relationship established in the antiviral effect study with different doses/regimens in Study GS-US-218-0103.

In Study GS-US-218-0103, a 5-day treatment regimen of presatovir (50 mg single dose on Dose Day 1, followed by 25 mg once daily on Dose Days 2 through 5) resulted in a significant reduction in RSV viral load. The mean AUC of RSV viral load as measured by the RT-qPCR assay from first viral load measurement post initial dose of study drug through end of quarantine (Day 12) was significantly lower in presatovir subjects compared to placebo subjects ($\Delta = 506.9 \log_{10} \text{PFUe} \cdot \text{hour/mL}$, $p < 0.001$). This 5-day regimen achieved presatovir trough concentrations ~4-5 fold higher than the paEC_{95} (52 ng/mL) for up to 120 hours following dose initiation for RSV M37 (virus strain used in GS-US-218-0103 study).

The dose for the current study was selected with the goal to maintain the plasma trough concentration of presatovir at least 5-fold above the paEC_{95} (25 ng/mL) of the clinical RSV isolates for the duration of RSV shedding in LT patients. Longitudinal viral dynamics data in LT patients with RSV is limited and is reported as a part of randomized trials and epidemiologic studies. Two trials indicate the majority of patients shed RSV for an average of 5.5 days {[Zamora et al 2011](#)} {[Simon et al 2012b](#)} {[Simon et al 2012a](#)}; however, the time of enrollment from onset of symptoms was variable and in some cases substantial. Moreover, immunosuppressed patients with RSV infection are demonstrated to shed virus for 21 days or longer {[Chemaly et al 2014](#)} {[Lehners et al 2013](#)} {[Geis et al 2013](#)}. The dose and schedule in the current study, 200 mg on Day 1/Baseline followed by 100 mg daily on Days 2 through 14, will maintain plasma levels of presatovir greater than 5-fold above paEC_{95} for at least 18 days after the first dose.

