4.3. Exclusion Criteria

Subjects who meet *any* of the following exclusion criteria are not to be enrolled in this study.

Related to concomitant or previous medication use:

- 1) Use of any non-marketed (according to region) investigational agents within 30 days, **OR** use of any investigational monoclonal anti-RSV antibodies within 4 months or 5 half-lives of Screening, whichever is longer, **OR** use of any prior investigational RSV vaccines

- 2) Use of a strong or moderate cytochrome P450 enzyme (CYP) inducer including but not limited to rifampin, St. John's Wort, carbamazepine, phenytoin, efavirenz, bosentan, etravirine, modafinil, and nafcillin, within 2 weeks prior to the first dose of IMP
- 3) Use of any of the following lympholytic treatment within the stated time frame:
anti-thymocyte globulin (ATG), < 3 months; anti-lymphoblast globulin (ALG), < 3 months;
muromonab-CD3 (OKT3), < 3 months; rituximab < 6 months; alemtuzumab < 9 months

Related to transplant history:

- 4) Recipient of any other organ transplant prior to Screening, with the exception of a LT (single or double) or heart/lung transplant
- 5) Recipient of a hematopoietic cell transplant at any time
- 6) Presence of BOS Stage 3 at Screening defined as a FEV₁ of 50% or less of baseline

Related to medical condition at Screening:

- 7) Respiratory failure requiring invasive mechanical ventilation
- 8) Evidence of shock requiring vasopressors
- 9) Known viral coinfection (including but not limited to influenza, metapneumovirus, human rhinovirus, parainfluenza, cytomegalovirus, or coronavirus) in the upper or lower respiratory tract \leq 14 days prior to Screening unless discussed with the medical monitor and deemed acceptable
- 10) Active systemic infection or infectious pneumonia of any etiology (ie, bacterial, viral [other than RSV] or fungal), including aspiration pneumonia, that is considered clinically significant by the investigator unless discussed with the medical monitor and deemed acceptable
- 11) Pregnant or lactating females
- 12) Evidence of recent and rapidly deteriorating lung function, occurring before the onset of the current viral respiratory infection, including but not limited to: acute lung allograft rejection, rapidly-progressive CLAD, and rCLAD (as determined by the investigator)
- 13) Any condition which, in the opinion of the investigator, would prevent full participation in this study or would interfere with the evaluation of the trial endpoints

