5.4. Prior and Concomitant Medications

Strong and moderate inducers of CYP enzymes may reduce the exposure of presatovir. Pharmacokinetic results from a clinical drug-drug-interaction study (GS-US-218-1409) demonstrated that induction of CYP enzymes with rifampin or efavirenz resulted in an 82% or 56% decrease, respectively, in presatovir AUC_{inf}. Therefore, concomitant administration of strong or moderate CYP inducers {FDA 2012} (including but not limited to rifampin, St John's Wort, carbamazepine, phenytoin, efavirenz, bosentan, etravirine, modafinil, and nafcillin) is excluded to avoid potential drug resistance.

Based on the results of Phase 1 studies with multi-transporter inhibitor cyclosporine and a potent CYP3A inhibitor, cobicistat, presatovir may be, coadministered with inhibitors of P-gp, BCRP, OATP 1B1, OTAP1B3 or CYP3A without dose modification.

When co-administered with renally eliminated concomitant medications (ie, filtration plus secretion), presatovir may increase the exposures of substrates secreted by the MATEs transporters, such as ganciclovir, acyclovir, levofloxacin, metformin, captopril, procainamide, fexofenadine, cimetidine, cephadrine, and cephalexin. Dosing and safety monitoring should be consistent with prescribing information, in particular for agents which require dose reductions in the setting of renal impairment.

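### The Per Protocol set has no criterion for subjects who first start a strong or moderate CYP inducer during dosing, although Protocol 5.4 excludes that use

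*SAP*

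**What the plan says.** SAP 3.1.3 builds the PP set from the FAS. It removes subjects who violated exclusion criteria 2, 16, 17 or 18 or inclusion criterion 3, subjects who missed more than 2 "doses (4 tablets) over the course of treatment", and subjects who missed 3 or more nasal swabs. The inducer item reads "EC #2: Use of a strong or moderate cytochrome P450 enzyme (CYP) inducer within 2 weeks prior to drug dosing". Protocol 4.3, which defines that criterion, closes the window at the first dose: "modafinil, and nafcillin, within 2 weeks prior to the first dose of IMP".

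The section adds: "The PP Analysis Set is the secondary analysis set for efficacy analyses". SAP 6.1.3 and 6.2.3 use the PP set for sensitivity analyses of the primary endpoint and both secondary endpoints.

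Inducers taken during dosing are covered elsewhere. Protocol 5.4 excludes "concomitant administration of strong or moderate CYP inducers" after reporting that rifampin or efavirenz "resulted in an 82% or 56% decrease", respectively, in AUCinf. Protocol 1.2.4.5 concludes: "Co-administration of moderate or potent inducers of CYP3A is not recommended". Protocol 1.4 sets the exposure goal, which is to "maintain the plasma trough concentration of presatovir at least 5-fold above" a paEC95 of 25 ng/mL.

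**The concern.** A PP set is meant to show the effect in subjects treated as the protocol intended. This one treats inducer use as serious enough to exclude a subject when it falls before the first dose. It then has no rule for the period when presatovir is being taken and an inducer can lower its level. A presatovir subject who newly starts a prohibited inducer stays in the set with reduced exposure. If the antiviral effect depends on exposure, keeping that subject dilutes the PP estimate. The PP result is the plan's main check on the FAS result, so a reader would take it as free of such cases when it need not be.

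**Working it through.** **1. Does any other text close the gap?**

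- SAP 3.1.3: the SAP says drug dosing where Protocol 4.3 says the first dose, but it cites exclusion criterion 2, so it remains an entry criterion. The two post-entry criteria (missed doses, missed swabs) do not detect a medication.
- Protocol 7.7.2.2: inappropriate use of a prohibited concomitant medication may be documented as a protocol deviation.
- SAP 4.3: post-entry deviations are summarised and listed. Nothing ties them to PP membership. Protocol 8.3 leaves the rules for major and minor deviations to the SAP, and SAP 4.3 states none.
- SAP 7.4.2: concomitant medications are summarised and listed only.

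The gap stands for new starts during dosing.

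**2. Internal consistency of the PP rules.** The regimen is 4 + 13 × 2 = 30 tablets. Missing 3 maintenance doses is 6/30 = 20% of planned drug and removes the subject. A co-medication that cuts AUCinf by 56% to 83% does not.

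**3. Exposure under established induction.** Inputs:

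- 25 mg daily gave troughs 4 to 5 times 52 ng/mL (Protocol 1.4), that is 208 to 260 ng/mL.
- Exposure is roughly dose-proportional, and the multiple-dose half-life is about 36 h (Protocol 1.2.4.1).
- Rifampin: AUCinf down about 83% in Protocol 1.2.4.5 and 82% in Protocol 5.4; half-life 13.4 h.
- Efavirenz: AUCinf down 56%; half-life 17.9 h.
- Target: 5 × 25 = 125 ng/mL.

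For a one-compartment model at steady state, trough/Cavg = kτr/(1 − r), with k = ln 2/half-life, τ = 24 h and r = exp(−kτ).

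| Case | Trough/Cavg | Cavg (ng/mL) | Trough (ng/mL) |
|---|---|---|---|
| No inducer, 100 mg | 0.787 | 1058 to 1322 | 832 to 1040 |
| Rifampin, −83% | 0.505 | 0.17 × above | 91 to 113 |
| Rifampin, −82% | 0.505 | 0.18 × above | 96 to 120 |
| Efavirenz, −56% | 0.606 | 0.44 × above | 282 to 353 |

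Check against the plan's own figure: without an inducer, the model stays above 125 ng/mL until about Day 19, in line with the at least 18 days stated in Protocol 1.4.

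Only rifampin falls below 125 ng/mL. Its troughs are still 91/25 = 3.6 to 120/25 = 4.8 times the paEC95.

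**4. Effect on the PP estimate.** The documents give no rate of on-treatment inducer use. Assume a PP presatovir arm of about 30 and the planning difference of 1.2 log. One subject who loses the whole effect moves the mean difference by 1.2/30 = 0.04 log; three would move it by 0.12 log. For scale, the standard error of the difference at the planned 34 versus 17 with SD 1.2 is 1.2 × √(1/34 + 1/17) = 0.36 log, so one subject is worth about 0.04/0.36 = 0.11 standard errors.

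**The case against.** The best counter-argument concerns scope and size. Most of it stands.

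- **Scope.** A reader might infer that the PP set ignores inducers during treatment altogether. It does not. Exclusion criterion 2 already removes anyone who used one in the 2 weeks before the first dose, including long-term users who continue. Only new starts remain, and for the two Day 7 endpoints only starts before the Day 7 assessment matter.
- **Exposure loss.** A reader might infer that an inducer begun on Day 2 removes presatovir exposure at once. The documents do not support that. The interaction figures come from multiple inducer doses, and the loading dose would already be on board, so loss within the Day 7 window may be partial. Figures exist for rifampin and efavirenz only, not for the other listed inducers.
- **Loss of effect.** Total loss is an extreme case. In the challenge study, 10 mg followed by 5 mg daily still gave a significant viral-load result (Protocol 1.2.4.7). On the same dose-proportional scaling, 5 mg daily gives troughs of 208/5 to 260/5, about 42 to 52 ng/mL, below the rifampin case. Those were healthy volunteers, and an exposure response was noted, so some loss remains plausible.
- **Visibility.** Concomitant medications and deviations are listed by subject, and PK is sampled pre-dose on Days 7 and 14. Affected subjects can be found, but no rule removes them.

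These points limit how much the gap could matter. They do not close it.

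**Conclusion.** The PP definition is incomplete: it screens for inducer use before dosing and not for new use during dosing, which Protocol 5.4 excludes. The severity is minor. The number of affected subjects is unknown and may be zero. About 0.04 log per subject is an upper bound, resting on the assumed 1.2 log effect, an arm of about 30 and complete loss of effect. The below-target trough holds for rifampin only. It assumes dose proportionality up to 100 mg daily, one-compartment kinetics and established induction.

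A reader might go further and infer that the trial's main result is at risk. It is not: the co-primary FAS tests, the alpha split and the gatekeeping do not use the PP set. Nor is criterion 2 wrong in itself; it is reasonable but does not reach far enough.

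**What to change.** Add one criterion to SAP 3.1.3, in line with Protocol 5.4: the subject took no strong or moderate CYP inducer from the first through the last dose of study drug. Identify such use from the WHO-coded concomitant-medication data, in both arms, before the blind is broken, as SAP 3.1 already requires for all analysis sets. The list in Protocol 5.4 is not exhaustive, so fix the working list of inducers at the same time. A single window over the whole treatment period, as the missed-dose criterion uses, keeps one PP set for all endpoints.

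The cost is one SAP line and a blinded medication review, with no new data. A few subjects may leave the PP set, including some whose inducer began after Day 7 and could not have affected the Day 7 endpoints. It is also one more exclusion on a post-randomisation event, which may be related to clinical course; the existing missed-dose rule has the same weakness. The FAS, alpha allocation and sample size do not change. The 82% and 83% rifampin figures in Protocol 5.4 and 1.2.4.5 should be reconciled in passing.
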